Confirmed eligibility. The initial database of eligible potential participants will be integrated with an extract of HIV surveillance data from the Virginia Department of Health. The integrated data will be used to confirm HIV status of eligible potential participants, their current/prior ART prescription(s) from state health department program databases, and potential participant eligibility for the study. Authorized Virginia Medicaid personnel will securely transfer the initial database of eligible potential participants to the Virginia Department of Health per an existing Interagency Agreement. Data integration and potential program participant eligibility will occur on a monthly basis during the enrollment period. After data transfer, authorized VCU personnel will use deterministic and probabilistic methods to link the two databases using the following variables: first and last name, social security number, complete or partial address, race/ethnicity, sex at birth, and date of birth. We note that complete information about current or prior ART prescriptions, which we are using to confirm potential participant eligibility where possible, is not available for all Virginians living with HIV; this is because only some Virginians have accessed state programs providing antiretroviral prescriptions. Given Medicaid’s comprehensive ART prescription coverage, we anticipate that Virginia Department of Health databases with ART prescription will be used primarily to ascertain if a potential participant has previously received ART prescriptions.

Recruitment

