Certified letter. The linkage coordinator will offer to mail a certified letter about the study to eligible potential participants who are successfully contacted but do not verify their identity. The letter is intended to legitimize the study and personalize contact with the potential participant. The certified letter will be similar to the mailed introductory letter, although it will have the option to include some tailored language referencing a prior conversation between the eligible potential participant and the linkage coordinator. The letter will include safeguards—including a general description about the nature of the study and general study team contact information—to protect confidentiality and minimize the risk of HIV status disclosure. Eligible potential participants who are sent a certified letter will be re-contacted by the linkage coordinator according to procedures described above.

Procedures: Usual care arm

The Usual Care arm will involve an artificial control sample created through propensity score matching. No contact will occur with these individuals and they will receive no study-specific intervention, consistent with state-level care for late ART prescription refill(s) for Virginia Medicaid enrollees living with HIV in Virginia. Detail for other processes and procedures for this arm are below.

Screening. Screening for controls will occur over the month enrollment period and as described above.

Recruitment. Recruitment of eligible potential participants in the control (Usual Care arm) does not apply. No contact will occur with these individuals.

Informed consent. Informed consent procedures do not apply. Only existing, secondary health information will be used. This health information will be de-identified, with no code key available; consent and HIPAA authorization do not apply.

Follow-up. A 3-month follow-up period will begin on the first date an eligible control is confirmed as having a late ART prescription refill(s) by >30–365 days.

Procedures: Program arm

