Phase 1. Phase 1 is for participants with late ART prescription refill(s) by >30–60 days. The phone consultation will involve a 30-minute discussion of the participant’s barriers to filling their ART prescription and referrals to resources that may address these barriers. The consultation will use a conversational format guided by scripted prompts. During the consultation, the linkage coordinator will document data on each participant’s self-reported barriers to filling ART prescriptions. Referrals will be made to existing resources that are already offered through the participant’s Medicaid managed care organization or through pharmacists, their HIV provider, or local community resources. If a participant self-reports multiple barriers to filling ART prescriptions, the participant will be asked to prioritize the barriers; this will allow the linkage coordinator to provide referral information that aligns most closely with participant preferences. Whenever possible, the primary referral will involve a warm hand-off, where the linkage coordinator introduces the participant directly to the referral resource in real-time. This approach is designed to engage the participant and maximize success in the referral process. If a warm hand-off is not possible at the time of the consultation, a follow-up call can be scheduled to make the warm hand-off; referral contact information will be offered to the participant after 3 unsuccessful warm hand-off attempts. Participants will additionally be given contact information for referrals involving 1-2 other prioritized barriers. The referral resource, referral date, and referral time will be documented by the linkage coordinator. Approximately ten business days after the Phase 1 referral, the participant’s ART prescription claims will be followed in the Medicaid claims data. The 10-business-day threshold will allow adequate time for an ART prescription fill and prescription claim reimbursement. If the participant has an ART prescription claim after this 10-business-day period, the participant will not be contacted further. If the participant has no ART prescription claim after the 10-business-day period, the participant will be eligible for Phase 2.

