Phase 2. Phase 2 is for participants with late ART prescription refill(s) by >60 days. Phase 2 will involve a more intensive phone consultation, in which more complex barriers may be assessed. Three phone contact attempts will be made in the same manner as in Phase 1. Participants who do not respond to these contact attempts, who do not verify their identities, or who do not either consent to participate or assent to continue to participate will not be contacted further. The linkage coordinator will guide a 30-minute consultation similar in format to Phase 1. In Phase 2, however, more complex barriers, such as substance use and mental health concerns, will be probed and referrals made accordingly. Participants in Phase 2 will also be offered PositiveLinks, an evidence-based mobile app designed to support ART adherence and retention in care (<https://www.positivelinks4ric.com/>). PositiveLinks is based on theories of behavior change and provides 1) daily check-ins on mood, stress, and medication adherence, which promote self-monitoring; 2) educational resources for users; 3) direct messaging with study linkage coordinators; 4) an anonymous message board to connect with peers living with HIV to provide and receive social support; and 5) contact information for patients’ providers and pharmacies. A major strength of the app is its support of self-monitoring, which addresses intrapersonal barriers to ART adherence. The app contains data security measures designed to protect patient privacy and confidentiality (e.g., phone calls to providers made through the app do not appear in the phone’s call log). Further details on the app’s development, user functions, and security features are available in the uploaded supporting documents. We emphasize that all study participants will be enrolled in Virginia Medicaid, and contracted Medicaid managed care organizations provide smartphones for enrollees (see

<https://www.virginiamanagedcare.com/choose/compare-plans>); therefore, we do not anticipate that smartphone ownership will be a barrier to participants' enrolling in PositiveLinks.

Follow-up. A 3-month follow-up period will begin on the date of the final consultation (**Table 1**).

Table 1. Start date of 3-month follow-up for participants receiving patient-level support

Phase(s) received	Start of 3-month follow-up
Phase 1 only	Date of final phase 1 consultation
Phase 2 only	Date of final phase 2 consultation

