Phases 1 and 2	Date of final phase 2 consultation or joining of PositiveLinks*

* Most recent date will be selected; does not include direct messaging support provided via PositiveLinks.

Outcomes

Outcomes will be at the participant level. The primary outcome will be HIV viral suppression, defined as the most recent HIV RNA viral load <200 copies/mL at 3-month follow-up. In the usual care arm, 3-month follow-up will be the first date an eligible control is confirmed as having a late ART prescription refill(s) by >30–365 days; in the program arm, 3-month follow-up will be as shown in Table 1. The secondary outcomes will be adherence (defined as the proportion with ART prescription claims covering >90% of enrolled coverage days) and the number and percentage of participants reinitiating late ART prescription.

Statistical analysis

Descriptive statistics. We will evaluate the balance of demographics and other patient characteristics, as well as the measures between the 2 treatment groups (those enrolled in the Program arm, and those in the Usual Care [control] group). We will compare the means and medians of the continuous variables and test the differences between the treatment samples using t-tests and Kruskal-Wallis tests. Systemic differences between the enrolled participants enrolled and the control might introduce selection bias.

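### The primary-outcome text gives the start of follow-up as the 3-month time point, sets no specimen-date limits for the viral load, and leaves no workable rule for people without one

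*Combined protocol and SAP*

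**What the plan says.** **Outcome.** The Outcomes section defines the primary outcome as "HIV viral suppression, defined as the most recent HIV RNA viral load <200 copies/mL at 3-month follow-up". It gives no earliest or latest specimen date.

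**What 3-month follow-up means in Outcomes.** For controls: "In the usual care arm, 3-month follow-up will be the first date an eligible control is confirmed as having a late ART prescription refill(s" (the sentence goes on to give the lateness range). For participants: "in the program arm, 3-month follow-up will be as shown in Table 1". Table 1 is captioned and headed as a list of start dates. Its row for people who received both phases reads "Date of final phase 2 consultation or joining of PositiveLinks", whichever is later.

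**What it means in Procedures.** Usual care arm, Follow-up: "A 3-month follow-up period will begin on the first date an eligible control is confirmed". Program arm, Follow-up: "A 3-month follow-up period will begin on the date of the final consultation".

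**Missing viral loads.** The sample size section expects 30% of the sample to lack a viral load. It then says that, given the team's experience and the inclusion and Medicaid–health department matching protocols, missing data are not permitted. The Screening section lists the eligibility criteria, and a viral load is not among them. On linkage it says "The integrated data will be used to confirm HIV status of eligible potential participants", together with ART prescriptions and eligibility.

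**Analysis.** Propensity scores predict membership of the treatment group. Chi-squared tests compare proportions in the matched samples, and logistic regression adjusts for confounders.

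**The concern.** A viral load drawn before first program contact cannot respond to the program. If such values count as outcomes, the two arms are partly compared on their past and the effect is diluted. The Outcomes text permits this because it takes the most recent value and names only the date on which follow-up starts.

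The missing-data statement makes this worse. An undated most-recent value is one way to arrive at no missing data. Dropping untested people is another, and it selects on testing that happens after the program has begun and that the program may change. Counting them as not suppressed is a third, and it answers a different question. The plan does not choose among them. The propensity score models who is in the program arm, not who is tested, so it does not by itself remove selection on testing.

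The start dates also fall at different points in the two arms. Under Phase 1, "If the participant has no ART prescription claim after the 10-business-day period, the participant will be eligible for Phase 2", so for those who go on to Phase 2 the clock starts only after earlier program contact. A value drawn between a Phase 1 consultation and that later start is neither a clean baseline nor a follow-up outcome.

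**Working it through.** **1. Dates side by side.**

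| Arm | Procedures | Outcomes |
|---|---|---|
| Usual care | 3-month period begins on the confirmation date | 3-month follow-up is the confirmation date |
| Program | 3-month period begins on the final consultation or other Table 1 date | 3-month follow-up is as in Table 1 (start dates only) |

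The usual-care wording conflicts directly. The program-arm wording points to a table that holds no end or assessment date. Neither section says that the specimen must be dated within the period.

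**2. Inputs.** From the sample size section: 100 per arm, 50% suppressed in controls, difference 0.28 (hence 78%), 30% missing. The plan gives no significance level; I assume two-sided 0.05. The documents give no share of stale values and no testing rates by arm, so those below are assumptions.

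**3. Formula.** For equal arms of size n, let d = p2 − p1 and p̄ = (p1 + p2)/2. Then SE0 = √[2p̄(1−p̄)/n] and SE1 = √[p1(1−p1)/n + p2(1−p2)/n]. Power ≈ Φ[(d − 1.96·SE0)/SE1]; the other tail is negligible here.

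**4. The plan's own figures.** n = 100, 0.50 versus 0.78: SE0 = 0.0679, SE1 = 0.0649, (0.28 − 0.1331)/0.0649 = 2.26, power 98.8%. This agrees with the plan's greater than 80% only as an inequality. With 70 per arm, power is 94.0%, so the plan's 70% after missing data is not reproduced. Nor is its 350 per arm: 45 per arm give 80% power for 0.28. Those are separate problems and the present point does not depend on them.

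**5. Dilution by pre-program values.** Let a share f of both arms be scored on values that are 50% suppressed. The program rate becomes 0.50f + 0.78(1−f), the control rate stays at 0.50, and d = 0.28(1−f).

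| f (assumed) | Difference | Power, 100 per arm |
|---|---|---|
| 0 | 0.280 | 98.8% |
| 10% | 0.252 | 96.3% |
| 30% | 0.196 | 81.2% |
| 50% | 0.140 | 51.6% |

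**6. Choice of rule, 30% untested in each arm and testing unrelated to suppression.**
- Drop them: 0.78 − 0.50 = 0.28, n = 70 per arm, power 94.0%.
- Count them as not suppressed: 0.7 × 0.78 − 0.7 × 0.50 = 0.546 − 0.350 = 0.196, n = 100 per arm, power 80.1%.

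These are different estimands, not a right and a wrong estimate of one quantity.

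**7. Differential testing with no true effect (50% suppressed in both arms), hypothetical.**
- Missing counted as not suppressed, 80% tested in the program arm and 60% in control: 0.8 × 0.5 − 0.6 × 0.5 = +0.10, significant 31.6% of the time.
- Complete-case; control tests 70% of suppressed and 50% of unsuppressed, program tests 80% of both. Control shows 0.35/0.60 = 58.3%, program 50.0%: −8.3 points. With 80 versus 60 tested and size-weighted pooling, significant 16.3% of the time.
- Complete-case; program tests 90% and 70%, control 60% of both. Program shows 0.45/0.80 = 56.25%, control 50.0%: +6.3 points, significant 11.3% of the time.

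If testing is unrelated to suppression within each arm, complete-case analysis is unbiased.

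**The case against.** **The intent is recoverable.** Both Procedures sections describe a period that begins on the listed dates, Table 1 is labelled as start dates, and the natural reading of the outcome is the last value as of month 3. This stands. A reader might infer that the plan measures the outcome at baseline; the documents do not support that. They support a narrower statement: the wording that defines the primary outcome conflicts with Procedures, and even the charitable reading supplies no earliest specimen date and no rule for someone with no specimen in the period.

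**The matching protocols may settle missingness.** The sentence cites protocols that may not be fully reproduced here, and it may mean restriction to complete data or replace the 30% estimate. Either is possible. As written it is unexplained, contradicts the figure just before it, and finds no support in Screening.

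**The magnitudes are hypothetical.** This also stands. At 30% stale values power is still 81.2%, above the plan's 80%. The differential-testing examples go both ways, so a reader who infers a known direction of bias goes beyond the documents.

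**The planned regression already helps.** With only the outcome missing, covariate-adjusted complete-case regression rests on much the same assumption as imputation on those covariates, so preferring imputation is a matter of taste. Neither removes bias when testing depends on suppression itself after adjustment, which is how the complete-case examples in step 7 arise. What either would gain is baseline viral load, which the plan does not name as a covariate.

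**Conclusion.** The point holds and needs correcting before analysis. It concerns the rule for the primary outcome, and an analyst could score pre-program viral loads without departing from the Outcomes text. The 30% expectation and the statement that no data may be missing cannot both guide the analysis, and no stated criterion makes the second true.

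The size is unknown because the documents give neither the share of stale values nor testing rates by arm. Under the assumed shares, the loss runs from slight (0.252, power 96.3%, at 10%) to about half the effect (0.140, power 51.6%, at 50%). This assumes that stale values are 50% suppressed, a figure borrowed from the plan's control outcome rate. The choice between dropping untested people and counting them as not suppressed alone moves the difference from 0.28 to 0.196 at 30% untested. Bias from differential testing is possible in either direction and is not established. Confidence is high on the conflicts in the text and low on how much they would matter in practice.

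**What to change.** 1. **Dates.** In Outcomes, say that follow-up starts on the listed dates, in line with both Procedures sections and Table 1. Define the outcome as the last viral load with a specimen date after that start and within the 3-month period, with one fixed allowance of the same length in both arms. State that the start event differs by arm, so the windows match in length only.
2. **Baseline.** Never score a value drawn before the start of follow-up as the outcome. Take baseline viral load from before confirmed eligibility in both arms and use it as a covariate.
3. **Missing outcomes.** Replace the no-missing-data sentence with one prespecified rule that reconciles it with the 30% estimate. Covariate-adjusted analysis or imputation, either including baseline viral load, would serve, with complete-case and missing counted as not suppressed as sensitivity analyses. Report the percentage tested by arm. State that none of these removes bias if testing depends on suppression itself after adjustment.
4. **Data step.** Control data are to be de-identified with no code key (Procedures: Usual care arm, Informed consent), and no section names the source of the viral loads. Name it, and attach dated baseline and follow-up values to controls before de-identification, since afterwards this may be impossible.

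**Cost.** Text changes in Outcomes, Statistical analysis and the sample size section, one data step and a small amount of added analysis. There will be fewer directly observed outcomes, by an amount the documents do not allow to be estimated. No clinical procedure changes.

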We will use propensity score methods to control for potential confounding patient or provider characteristics that may affect the acceptance to enroll in the study and, consequently, the outcome of interest (HIV viral suppression, adherence, and reinitiation). Propensity score methods help us balance the distribution of the covariates between treatment and control groups, reducing the selection bias and allowing for more accurate causal inference when assessing the impact of the treatment. Propensity scores (PS) will be calculated as the predicted probabilities of being in the treatment group. Logistic regression model predicting being in the enrolled in the study will be used. A wide range of patient (age, gender, race, Medicaid enrollment, etc.), provider (specialty), hospital and geographical (region, rurality) characteristics will be considered in the regression model. We will use the PS to match the treatment group to the control group. We will calculate the inverse probability weights (IPW) using these PS. We will evaluate the effect of the program in the PS matched samples on the binary outcomes—including HIV RNA viral load <200 copies/mL (primary outcome), adherence (secondary outcome), and reinitiation (secondary outcome)—by comparing the proportions between the Program arm and the Usual Care arm. We will use Chi-squared tests to evaluate the statistical significance of the effects of treatments on proportions. We will also use logistic regression models to test for the program effects, adjusting for all potential confounders that might affect the outcome and bias the results.

Sample size and statistical power considerations

We expect to enroll 100 participants in the Program arm. This sample size provides adequate power to detect differences in HIV viral suppression (i.e., HIV viral load <200 copies/mL), the primary outcome, across arms. Assuming a 50% rate of viral suppression in the control group, with 100 subjects in the control group, we will be able to detect a difference of .28 in the rate of viral suppression with greater than 80% power. This requires a sample size of 350 participants in each arm. However, an estimated 30% of the sample will be missing HIV viral load data (Crepaz et al. *MMWR Morb Mortal Wkly Rep* 2018). This translates into dropping the power to 70%. According to our experience with these data, and the

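### The only balance method named is significance testing of continuous covariates; no method is given for categorical covariates, and no check is stated after matching or weighting

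*Combined protocol and SAP*

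**What the plan says.** The descriptive-statistics paragraph of the Statistical analysis section opens with a general commitment: "We will evaluate the balance of demographics and other patient characteristics". The method follows in one sentence: "We will compare the means and medians of the continuous variables" and "test the differences between the treatment samples using t-tests and Kruskal-Wallis tests". The paragraph ends by acknowledging that systematic differences between the arms could cause selection bias.

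The next paragraph describes the propensity model: "A wide range of patient (age, gender, race, Medicaid enrollment, etc.), provider (specialty), hospital and geographical (region, rurality) characteristics will be considered". The scores are then used for matching, and inverse probability weights are also calculated from them. Chi-squared tests are mentioned only for outcomes: "We will use Chi-squared tests to evaluate the statistical significance of the effects of treatments on proportions". A logistic regression of outcome, adjusted for the variables thought likely to confound, is listed in addition.

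The section on the usual care arm confirms that the controls are built by propensity matching, with no contact and no randomisation. On size, the sample-size section says "We expect to enroll 100 participants in the Program arm" and does its calculation "with 100 subjects in the control group".

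Nowhere does the plan give a standardized difference, a limit for acceptable imbalance, a statement of whether balance is assessed before or after matching, or a step to follow if the match is poor.

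**The concern.** Program participants are those who were reached and consented; controls are selected by a model. Whether the match made the arms comparable on measured covariates is a question about the size of the remaining differences in this sample. A p-value answers a different question, and its answer depends on the number of subjects. In a small matched sample, a non-significant test is compatible with a difference large enough to matter.

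Categorical covariates are a second gap. Gender, race, specialty, region and rurality are naturally categorical, and neither named test suits a nominal variable. A third is timing: without a stated check in the matched sample, and another in the weighted sample if the weights are used, nothing in the plan shows whether the propensity step worked. Imbalance left in a prognostic covariate would carry straight into any unadjusted comparison of viral suppression.

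**Working it through.** The plan gives no operating figure for its balance tests, so there is nothing of its own to reproduce here. The check asks how often the named tests would flag a given imbalance.

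**Inputs.** n = 100 per arm (sample-size section; equal arms are implied, but the matching ratio is not stated). Alpha = 0.05 two-sided (assumed). Underlying SMD d from 0.10 to 0.40 (assumed range; the plan sets no threshold).

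**t-test.** Power = P(|T| > t_crit), where T is noncentral t with 2n − 2 = 198 degrees of freedom and noncentrality d × √(n/2) = 7.07 × d. For d = 0.10, 0.20 and 0.25 the noncentrality is 0.71, 1.41 and 1.77.

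| SMD | 100 per arm | 70 per arm | 350 per arm |
|---|---|---|---|
| 0.10 | 10.8% | 9.0% | 26.2% |
| 0.20 | 29.1% | 21.7% | 75.2% |
| 0.25 | 42.1% | 31.2% | 91.0% |
| 0.30 | 56.0% | 42.2% | 97.7% |
| 0.40 | 80.4% | 65.2% | about 100% |

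The other two columns are there because the sample-size section also states 350 per arm, which conflicts with its 100, and expects 30% of viral loads to be missing (100 × 0.70 = 70). The 70 column applies only if balance is checked in subjects with a viral load; the same section also says that no missing data are allowed.

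**Where detection becomes likely, 100 per arm (normal approximation).** 50%: 1.96 × √(2/100) = 0.277. 80%: (1.96 + 0.842) × √(2/100) = 0.396. At 350 per arm the 50% point is 1.96 × √(2/350) = 0.148. Judging balance by p < 0.05 is therefore close to using an SMD cut-off of 0.28 at one sample size and 0.15 at the other, with neither chosen for its relevance to bias. For 80% power, an SMD of 0.10 needs 1,570 per arm and 0.20 needs 393.

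**Kruskal-Wallis.** With two groups and a normal shift, efficiency relative to the t-test is about 3/π, so 100 per arm acts like 95.5. Approximate power is 10.6%, 28.0% and 40.5% at SMD 0.10, 0.20 and 0.25.

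**Would chi-squared balance tests close the categorical gap?** No. At 100 per arm, 50% versus 55% (SMD 0.10) is flagged about 10.5% of the time and 50% versus 60% (SMD 0.20) about 29%.

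**The case against.** Several points on the other side stand.

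- The plan does not rely on matching alone. The adjusted logistic model covers measured confounders, categorical ones included, so residual imbalance in those would mainly affect the unadjusted chi-squared comparison. It is still listed as an additional analysis, and it does not show whether the match succeeded.
- A reader might infer that categorical covariates will go unchecked. The documents do not support that: they promise a balance evaluation of demographics and other characteristics generally. What is missing is a named method.
- A reader might infer that a non-significant test would lead to the match being accepted and the propensity model left alone. No such rule is written. The tests appear under descriptive statistics, ahead of the propensity step, and may be meant only as description, alongside a comparison of means and medians that is itself about magnitude. If so, the plan has no stated check of match adequacy at all.
- The tests do not miss every imbalance of note: at 100 per arm they detect an SMD of 0.30 in 56% of cases and 0.40 in 80%.
- A hard SMD limit would be unreasonable here. The standard error of an SMD at 100 per arm is about √(2/100) = 0.14, so even under perfect randomisation P(|Z| > 0.10/0.141) = P(|Z| > 0.71), or about 48% of covariates, would exceed 0.10.

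**Conclusion.** The point holds as a specification gap with a better method available at almost no cost. The only named balance method covers continuous variables. No method is named for categorical covariates, and no balance check is stated after matching or weighting. At 100 per arm and a two-sided 5% level, both assumed to apply to these tests, the named tests would miss 58% to 89% of imbalances with an SMD between 0.25 and 0.10. At 350 per arm they would still miss about 74% at 0.10, but only 25% at 0.20.

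A reader might go further and infer a material inflation of false positives in the primary comparison. That depends on assumptions the documents do not supply. A 0.25 SD imbalance in a 50% binary predictor is 0.25 × 0.5 = 12.5 points. If the predictor shifts suppression by 40 points, the bias is 0.125 × 0.40 = 5 points. With standard error √(2 × 0.25/100) = 0.071, the false-positive rate is then about 10.9%. With a 20-point predictor the bias is 2.5 points and the rate about 6.4%; with a 10-point predictor, about 5.4%. With the 40-point predictor but an SMD of 0.10, the bias is 2 points and the rate about 5.9%. All of these assume no covariate adjustment, so the largest figure is an extreme case and not an expected one.

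**What to change.** In the Statistical analysis section, replace the t-tests and Kruskal-Wallis tests as the balance measure with the following:

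- Report SMDs for every covariate in the propensity model, each level of a categorical covariate included, and variance ratios for continuous ones.
- Report them before matching, after matching, and in the inverse-probability-weighted sample if the weights are used.
- Review them before outcomes are opened.
- Prespecify a limit, for example an SMD of 0.10, as a prompt to try respecifying the propensity model. It should not be a condition that every covariate must meet.
- Keep any covariate still above the limit in the adjusted outcome model, and report its residual SMD beside the unadjusted comparison.

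The cost is a paragraph of SAP text, routine software output, and some re-running of the match before outcomes are opened. No participant procedure changes.
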